5.1.3 Lifestyle Considerations

5.1.3.1 Meals and Dietary Restrictions

Participants are prohibited to consume grapefruit juice while on olaparib therapy.

Participants should maintain a normal diet unless modifications are required to manage an AE such as diarrhea, nausea or vomiting.

5.1.3.2 Contraception

Pembrolizumab may have adverse effects on a fetus in utero. Refer to Appendix 3 for approved methods of contraception.

5.1.4 Pregnancy

If a participant inadvertently becomes pregnant while on treatment with pembrolizumab and/or olaparib, the participant will be immediately discontinued from study intervention(s). The site will contact the participant at least monthly and document the participant's status until the pregnancy has been completed or terminated. The outcome of the pregnancy will be reported to Merck within 2 working days if the outcome is a serious adverse experience (e.g. death, abortion, congenital anomaly, or other disabling or life-threatening complication to the mother or newborn). The study Investigator will make every effort to obtain permission to follow the outcome of the pregnancy and report the condition of the fetus or newborn to Merck.

5.1.5 Use in Nursing Women

It is unknown whether pembrolizumab or olaparib is excreted in human milk. Since many drugs are excreted in human milk, and because of the potential for serious adverse reactions in the nursing infant, participants who are breast-feeding are not eligible for enrollment.

5.2 Trial Intervention(s)

The intervention(s) to be used in this trial is outlined below in Table 2

Table 2 Trial Intervention(s)

Drug	Dose/Potency	Dose Frequency	Route of Administration	Regimen/Treatment Period	Use
Pembrolizumab	200 mg	Q3W	IV infusion	Day 1 of each 3-week cycle	Experimental
Olaparib tablet	300 mg	Twice Daily	Oral	Daily	Experimental

Trial intervention(s) should begin as close as possible to the date on which intervention is assigned.

5.2.1 Timing of Dose Administration

Trial interventions should be administered on Day 1 of each cycle after all procedures/assessments have been completed as detailed on the Trial Flow Chart (Section 6.0). Trial interventions may be administered up to 3 days before or after the scheduled Day 1 of each cycle due to administrative reasons.

All trial interventions will be administered on an outpatient basis.

Pembrolizumab 200 mg will be administered as a 30-minute IV infusion every 3 weeks. Sites should make every effort to target infusion timing to be as close to 30 minutes as possible. However, given the variability of infusion pumps from site to site, a window of -5 minutes and +10 minutes is permitted (i.e., infusion time is 30 minutes: -5 min/+10 min).

The Pharmacy Manual contains specific instructions for the preparation of the pembrolizumab infusion fluid and administration of infusion solution.

Pembrolizumab treatment may continue until 24 months of treatment or 35 doses of pembrolizumab, or disease progression, whichever occurs first.

Olaparib will be initiated on cycle 1 day 1 immediately following the completion of the first dose of pembrolizumab. Cycle 1 day 1 infusion should occur in the morning (AM) in order to receive 2 doses on day 1.

Olaparib tablets should be taken at the same time each day, approximately 12 hours apart with one glass of water. The tablets should be swallowed whole and not chewed, crushed, dissolved or divided. Olaparib tablets can be taken with or without food. If vomiting occurs shortly after the olaparib tablets

are swallowed, the dose should only be replaced if all of the intact tablets can be seen and counted. Should any patient enrolled on the study miss a scheduled dose for whatever reason (e.g., as a result of forgetting to take the tablets or vomiting), the patient will be allowed to take the scheduled dose up to a maximum of 2 hours after that scheduled dose time. If greater than 2 hours after the scheduled dose time, the missed dose is not to be taken and the patient should take their allotted dose at the next scheduled time.

Patients should be given clear instructions on how and when to take their study treatment. Patients will self-administer olaparib.

Any change from the dosing schedule, dose interruptions, dose reductions, dose discontinuations should be recorded in eCRF.

5.2.2 Dose Modification and toxicity management for immune-related AEs associated with Olaparib and/or Pembrolizumab

Olaparib Dose Modification

Olaparib Dose Reductions

In case a dose reduction is necessary, olaparib will be administered as follows:

Table 3a Dose reductions for study treatment to manage adverse events

Initial Dose	Following re-challenge post interruption: Dose reduction 1	Dose reduction 2
300 mg twice daily	250 mg twice daily	200 mg twice daily

Table 3b Dose reduction for study treatment if patient develops moderate renal impairment

Initial Dose	Moderate renal impairment (calculated creatinine clearance by Cockcroft -Gault equation or based on a 24 hour urine test between 31 and 50 ml/min): Dose reduction
300 mg twice daily	200 mg twice daily

Table 3c Dose reductions for study treatment if patient has to start taking a strong or moderate CYP3A inhibitor

Initial Dose	Strong CYP3A inhibitor	Moderate CYP3A inhibitor
300 mg twice daily	100 mg twice daily	150 mg twice daily

For guidance on dose reductions for management of AEs (including renal impairment), refer to section 6.2.

For guidance on dose reductions when concomitant strong or moderate CYP3A inhibitors cannot be avoided see section 6.5.

When dose reduction is necessary patients will take one 150 mg tablet and one 100 mg tablet twice daily or two x 100 mg tablet twice daily (see Section 8.4.6), or one 150 mg tablet twice daily or one 100 mg tablet twice daily (see Section 6.5).

Pembrolizumab Dose Modification

AEs associated with pembrolizumab exposure may represent an immunologic etiology. These immune-related AEs (irAEs) may occur shortly after the first dose or several months after the last dose of pembrolizumab treatment and may affect more than one body system simultaneously. Therefore, early recognition and initiation of treatment is critical to reduce complications. Based on existing clinical study data, most irAEs were reversible and could be managed with interruptions of pembrolizumab, administration of corticosteroids and/or other supportive care. For suspected irAEs, ensure adequate evaluation to confirm etiology or exclude other causes. Additional procedures or tests such as bronchoscopy, endoscopy, skin biopsy may be included as part of the evaluation. Dose modification and toxicity management guidelines for irAEs associated with pembrolizumab are provided in Table 4.

Table 4 Dose modification and toxicity management guidelines for immune-related AEs associated with pembrolizumab

General instructions:				

 Severe and life-threatening irAEs should be treated with IV corticosteroids followed by oral steroids. Other immunosuppressive treatment should begin if the irAEs are not controlled by corticosteroids. Pembrolizumab must be permanently discontinued if the irAE does not resolve or the corticosteroid dose is not \leq10 mg/day within 12 weeks of the last pembrolizumab treatment. The corticosteroid taper should begin when the irAE is \leq Grade 1 and continue at least 4 weeks. If pembrolizumab has been withheld, pembrolizumab may resume after the irAE decreased to \leq Grade 1 after corticosteroid taper. 				
irAEs	Toxicity grade (CTCAE V5.0)	Action with pembrolizumab	Corticosteroid and/or other therapies	Monitoring and follow-up
Pneumonitis	Grade 2	Withhold	
 Administer corticosteroids (initial dose of 1 - 2 mg/kg prednisone or equivalent) followed by taper Add prophylactic antibiotics for opportunistic infections 	
 Monitor participants for signs and symptoms of pneumonitis Evaluate participants with suspected pneumonitis with radiographic imaging and initiate corticosteroid treatment
	Grade 3 or 4, or recurrent Grade 2	Permanently discontinue		
Diarrhea / Colitis	Grade 2 or 3	Withhold	
 Administer corticosteroids (initial dose of 1 - 2 mg/kg prednisone or equivalent) followed by taper 	
 Monitor participants for signs and symptoms of enterocolitis (ie, diarrhea, abdominal pain, blood or mucus in stool with or without fever) and of bowel perforation (ie, peritoneal signs and ileus) Participants with \geqGrade 2 diarrhea suspecting colitis should consider GI consultation and performing endoscopy to rule out colitis Participants with diarrhea/colitis should be advised to drink liberal quantities of clear fluids. If sufficient oral fluid intake is not feasible, fluid and electrolytes should be substituted via IV infusion
	Grade 4 or recurrent Grade 3	Permanently discontinue		

AST or ALT elevation or Increased Bilirubin	Grade 2 ^a	Withhold	
 Administer corticosteroids (initial dose of 0.5 - 1 mg/kg prednisone or equivalent) followed by taper 	
 Monitor with liver function tests (consider weekly or more frequently until liver enzyme value returned to baseline or is stable)
	Grade 3 ^b or 4 ^c	Permanently discontinue	
 Administer corticosteroids (initial dose of 1 - 2 mg/kg prednisone or equivalent) followed by taper 	
Type 1 diabetes mellitus (T1DM) or Hyperglycemia	New onset T1DM or Grade 3 or 4 hyperglycemia associated with evidence of β -cell failure	Withhold ^d	
 Initiate insulin replacement therapy for participants with T1DM Administer anti-hyperglycemic in participants with hyperglycemia 	
 Monitor participants for hyperglycemia or other signs and symptoms of diabetes
Hypophysitis	Grade 2	Withhold	
 Administer corticosteroids and initiate hormonal replacements as clinically indicated 	
 Monitor for signs and symptoms of hypophysitis (including hypopituitarism and adrenal insufficiency)
	Grade 3 or 4	Withhold or permanently discontinue ^d		
Hyperthyroidism	Grade 2	Continue	
 Treat with non-selective beta-blockers (eg, propranolol) or thionamides as appropriate 	
 Monitor for signs and symptoms of thyroid disorders
	Grade 3 or 4	Withhold or permanently discontinue ^d		

Hypothyroidism	Grade 2, 3, or 4	Continue	
 Initiate thyroid replacement hormones (eg, levothyroxine or liothyronine) per standard of care Monitor for signs and symptoms of thyroid disorders
Nephritis and renal dysfunction: grading according to increased creatinine or acute kidney injury	Grade 2	Withhold	
 Administer corticosteroids (prednisone 1 – 2 mg/kg or equivalent) followed by taper Monitor changes of renal function
	Grade 3 or 4	Permanently discontinue	
Myocarditis	Grade 1 or 2	Withhold	
 Based on severity of AE administer corticosteroids Ensure adequate evaluation to confirm etiology and/or exclude other causes
	Grade 3 or 4	Permanently discontinue	
All Other immune-related AEs	Intolerable/persistent Grade 2	Withhold	
 Based on severity of AE administer corticosteroids Ensure adequate evaluation to confirm etiology or exclude other causes
	Grade 3	Withhold or discontinue based on the event ^e	
	Grade 4 or recurrent Grade 3	Permanently discontinue	

^a AST/ALT: >3.0 - 5.0 x ULN if baseline normal; >3.0 - 5.0 x baseline, if baseline abnormal; bilirubin:>1.5 - 3.0 x ULN if baseline normal; >1.5 - 3.0 x baseline if baseline abnormal

^b AST/ALT: >5.0 to 20.0 x ULN, if baseline normal; >5.0 - 20.0 x baseline, if baseline abnormal; bilirubin:>3.0 - 10.0 x ULN if baseline normal; >3.0 - 10.0 x baseline if baseline abnormal

^c AST/ALT: >20.0 x ULN, if baseline normal; >20.0 x baseline, if baseline abnormal;
bilirubin: >10.0 x ULN if baseline normal; >10.0 x baseline if baseline abnormal

^d The decision to withhold or permanently discontinue pembrolizumab is at the discretion of the investigator or treating physician. For participants with Grade 3 or 4 immune-related endocrinopathy where withhold of pembrolizumab is required, pembrolizumab may be resumed when AE resolves to \leq Grade 2 and is controlled with hormonal replacement therapy or achieved metabolic control (in case of T1DM)

^e Events that require discontinuation include but are not limited to: Guillain-Barre Syndrome, encephalitis, Stevens-Johnson Syndrome and toxic epidermal necrolysis.

Dose modification and toxicity management of infusion-reactions related to pembrolizumab

Pembrolizumab may cause severe or life-threatening infusion-reactions including severe hypersensitivity or anaphylaxis. Signs and symptoms usually develop during or shortly after drug infusion and generally resolve completely within 24 hours of completion of infusion. Dose modification and toxicity management guidelines on pembrolizumab associated infusion reaction are provided in Table 5.

Table 5 Pembrolizumab Infusion Reaction Dose modification and Treatment Guidelines

NCI CTCAE Grade	Treatment	Premedication at Subsequent Dosing
Grade 1 Mild reaction; infusion interruption not indicated; intervention not indicated	Increase monitoring of vital signs as medically indicated until the participant is deemed medically stable in the opinion of the investigator.	None
Grade 2 Requires therapy or infusion interruption but responds promptly to symptomatic treatment (e.g., antihistamines, NSAIDs, narcotics, IV fluids); prophylactic medications indicated for ≤ 24 hrs	
Stop Infusion.
 
Additional appropriate medical therapy may include but is not limited to:
 
IV fluids Antihistamines NSAIDs Acetaminophen Narcotics
 
Increase monitoring of vital signs as medically indicated until the participant is deemed medically stable in the opinion of the investigator. If symptoms resolve within 1 hour of stopping drug infusion, the infusion may be restarted at 50% of the original infusion rate (e.g. from 100 mL/hr to 50 mL/hr). Otherwise dosing will be held until symptoms resolve and the participant should be premedicated for the next scheduled dose.
 
Participants who develop Grade 2 toxicity despite adequate premedication should be permanently discontinued from further study drug intervention
	
Participant may be premedicated 1.5h (± 30 minutes) prior to infusion of _____ with:
 
Diphenhydramine 50 mg po (or equivalent dose of antihistamine). Acetaminophen 500-1000 mg po (or equivalent dose of analgesic).

Grades 3 or 4 Grade 3: Prolonged (i.e., not rapidly responsive to symptomatic medication and/or brief interruption of infusion); recurrence of symptoms following initial improvement; hospitalization indicated for other clinical sequelae (e.g., renal impairment, pulmonary infiltrates) Grade 4: Life-threatening; pressor or ventilatory support indicated	
Stop Infusion.
 
Additional appropriate medical therapy may include but is not limited to:
 
Epinephrine** IV fluids Antihistamines NSAIDs Acetaminophen Narcotics Oxygen Pressors Corticosteroids
 
Increase monitoring of vital signs as medically indicated until the participant is deemed medically stable in the opinion of the investigator. Hospitalization may be indicated.
 
**In cases of anaphylaxis, epinephrine should be used immediately.
 
Participant is permanently discontinued from further study drug intervention.
	No subsequent dosing

Appropriate resuscitation equipment should be available at the bedside and a physician readily available during the period of drug administration.
For further information, please refer to the Common Terminology Criteria for Adverse Events v5.0 (CTCAE) at <http://ctep.cancer.gov>

Other allowed dose interruption for pembrolizumab

Pembrolizumab may be interrupted for situations other than treatment-related AEs such as medical / surgical events or logistical reasons not related to study therapy. Participants should be placed back on study therapy within 3 weeks of the scheduled interruption, unless otherwise discussed with the Sponsor. The reason for interruption should be documented in the patient's study record.

5.3 Randomization or Treatment Allocation

This is a non-randomized trial.

5.4 Stratification

5.5 Concomitant Medications/Vaccinations (allowed & prohibited)

Medications or vaccinations specifically prohibited in the exclusion criteria are not allowed during the ongoing trial. If there is a clinical indication for one of these or other medications or vaccinations specifically prohibited during the trial, discontinuation from trial therapy or vaccination may be required. The final decision on any supportive therapy or vaccination rests with the investigator and/or the participant's primary physician. However, the decision to continue the participant on study intervention requires the mutual agreement of the investigator, the Sponsor, and the participant.

5.5.1 Acceptable Concomitant Medications

All treatments that the investigator considers necessary for a participant's welfare may be administered at the discretion of the investigator in keeping with the community standards of medical care. All concomitant medication will be recorded on the case report form (CRF) including all prescription, over-the-counter (OTC), herbal supplements, and IV medications and fluids. If changes occur during the trial period, documentation of drug dosage, frequency, route, and date may also be included on the CRF.

The use of any natural/herbal products or other traditional remedies should be discouraged, but use of these products, as well as any medication or vaccine including over-the-counter or prescription medicines, vitamins, and/or herbal supplements that the patient is receiving at the time of enrolment or receives during the study must be recorded along with:

- Reason for use
- Dates of administration including start and end dates
- Dosage information including dose and frequency

Anti-emetics/Anti-diarrheals

From screening Part 2 onwards, should a patient develop nausea, vomiting and / or diarrhea, then these symptoms should be reported as AEs (see section 8.3) and appropriate treatment of the event given.

All concomitant medications received within 28 days prior to the first dose of trial intervention and up to 30 days after the last dose of trial intervention should be recorded. Concomitant medications administered after 30 days after the last dose of trial intervention should be recorded for SAEs and Events of Clinical Interest (ECIs) as defined in Section 7.2.

5.5.2 Prohibited Concomitant Medications

Participants are prohibited from receiving the following therapies during the Screening and Treatment Phase (including retreatment for post-complete response relapse) of this trial:

- Antineoplastic systemic chemotherapy or biological therapy

Confidential

Page 30 of 87

- Immunotherapy not specified in this protocol
- Chemotherapy not specified in this protocol
- Investigational agents other than pembrolizumab and olaparib
- Radiation therapy

Note: Radiation therapy to a symptomatic solitary lesion or to the brain may be allowed at the investigator's discretion.

- Live vaccines within 30 days prior to the first dose of study treatment and while participating in the study. Examples of live vaccines include, but are not limited to, the following: measles, mumps, rubella, varicella/zoster, yellow fever, rabies, BCG, and typhoid vaccine. Seasonal influenza vaccines for injection are generally killed virus vaccines and are allowed; however, intranasal influenza vaccines (eg, FluMist®) are live attenuated vaccines and are not allowed.
- Systemic glucocorticoids for any purpose other than to modulate symptoms from an event of clinical interest of suspected immunologic etiology. The use of physiologic doses of corticosteroids may be approved after consultation with the Sponsor.

Participants who, in the assessment by the investigator, require the use of any of the aforementioned treatments for clinical management should be removed from the study. All treatments that the Investigator considers necessary for a participant's welfare may be administered at the discretion of the Investigator in keeping with the community standards of medical care.

Medications or vaccinations specifically prohibited in the exclusion criteria are not allowed during the ongoing study. If there is a clinical indication for any medication or vaccination specifically prohibited during the study, discontinuation from study therapy or vaccination may be required. The final decision on any supportive therapy or vaccination rests with the investigator and/or the participant's primary physician. However, the decision to continue the participant on study treatment requires the mutual agreement of the investigator, the Sponsor and the participant. However, the decision to continue the participant on study intervention requires the mutual agreement of the investigator, the Sponsor, and the participant.

Medications that may NOT be administered

Table 6 Prohibited medications

Prohibited medication/class of drug:	
Anticancer therapy:	Not permitted while the patient is receiving study medication
Chemotherapy	
Immunotherapy	
Hormonal therapy*	
Radiotherapy (except palliative)	
Biological therapy	
Other novel agents	
Live virus vaccines	Not permitted while the patient is receiving study medication and during the 30 day follow up period.
Live bacterial vaccines	An increased risk of infection by the administration of live virus and bacterial vaccines has been observed with conventional chemotherapy drugs and the effects with olaparib are unknown.

*Hormone Replacement Therapy (HRT) is acceptable

Restricted concomitant medications

Table 7 Restricted concomitant medications

Medication/class of drug:	Usage (including limits for duration permitted and special situations in which it's allowed):

Table 7 Restricted concomitant medications

Medication/class of drug:	Usage (including limits for duration permitted and special situations in which it's allowed):
Strong CYP3A inhibitors: itraconazole, telithromycin, clarithromycin, boosted protease inhibitors, indinavir, saquinavir, nelfinavir, boceprevir, telaprevir	Strong or moderate CYP3A inhibitors should not be taken with olaparib. If there is no suitable alternative concomitant medication then the dose of olaparib should be reduced for the period of concomitant administration. The dose reduction of olaparib should be recorded in the CRF with the reason documented as concomitant CYP3A inhibitor use.
Moderate CYP3A inhibitors: ciprofloxacin, erythromycin, diltiazem, fluconazole, verapamil	
 • Strong CYP3A inhibitors – reduce the dose of olaparib to 100 mg twice daily for the duration of concomitant therapy with the strong inhibitor and for 5 half lives afterwards. • Moderate CYP3A inhibitors - reduce the dose of olaparib to 150 mg twice daily for the duration of concomitant therapy with the moderate inhibitor and for 3 half lives afterwards. • After the washout of the inhibitor is complete, the olaparib dose can be re-escalated.
Strong inducers: phenobarbital, phenytoin, rifampicin, rifabutin, rifapentine, carbamazepine, nevirapine, enzalutamide and St John's Wort	Strong or moderate CYP3A inducers should not be taken with olaparib. If the use of any strong or moderate CYP3A inducers are considered necessary for the patient's safety and welfare this could diminish the clinical efficacy of olaparib.
Moderate CYP3A inducers: bosentan, efavirenz and modafinil	If a patient requires use of a strong or moderate CYP3A inducer then they must be monitored carefully for any change in efficacy of olaparib.

Table 7 Restricted concomitant medications

Medication/class of drug:	Usage (including limits for duration permitted and special situations in which it's allowed):

 • CYP3A4 substrates: hormonal contraceptive, simvastatin, cisapride, cyclosporine, ergot alkaloids, fentanyl, pimozide, sirolimus, tacrolimus and quetiapine • CYP2B6 substrates: bupropion, efavirenz • OATP1B1 substrates: bosentan, glibenclamide, repaglinide, statins and valsartan • OCT1, MATE1 and MATE2K substrates: metformin • OCT2 substrates: serum creatinine • OAT3 substrates: furosemide, methotrexate 	
Effect of olaparib on other drugs
 
Based on limited in vitro data, olaparib may increase the exposure to substrates of CYP3A4, OATP1B1, OCT1, OCT2, OAT3, MATE1 and MATE2K.
 
Based on limited in vitro data, olaparib may reduce the exposure to substrates of 2B6.
 
Caution should be observed if substrates of these isoenzymes or transporter proteins are co-administered.

Anticoagulant therapy	Patients who are taking warfarin may participate in this trial; however, it is recommended that international normalized ratio (INR) be monitored carefully at least once per week for the first month, then monthly if the INR is stable. Subcutaneous heparin and low molecular weight heparin are permitted.
Palliative radiotherapy	Palliative radiotherapy may be used for the treatment of pain at the site of bony metastases that were present at baseline, provided the investigator does not feel that these are indicative of clinical disease progression during the study period. Study treatment should be discontinued for a minimum of 3 days before a patient undergoes therapeutic palliative radiation treatment. Study treatment should be restarted within 4 weeks as long as any bone marrow toxicity has recovered.

Table 7 Restricted concomitant medications

Medication/class of drug:	Usage (including limits for duration permitted and special situations in which it's allowed):
Administration of other anti-cancer agents	Patients must not receive any other concurrent anti-cancer therapy, including investigational agents, while on study treatment. Patients may continue the use of bisphosphonates or denosumab for bone disease and corticosteroids for the symptomatic control of brain metastases provided the dose is stable before and during the study and they were started at least 4 weeks prior to beginning study treatment.

There are no prohibited therapies during the Post-Treatment Follow-up Phase.

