5.1.1 Participant Inclusion Criteria

Participants are eligible to be included in the study only if all of the following criteria apply:

1. Female participants who are at least 18 years of age on the day of signing informed consent with histologically confirmed diagnosis of cervical carcinoma will be enrolled in this study.
2. Cervical cancer is a disease of the female genital tract. No male patients will be enrolled.
3. A female participant is eligible to participate if she is not pregnant (see Appendix 3), not breastfeeding, and at least one of the following conditions applies:
 - a. Not a woman of childbearing potential (WOCBP) as defined in Appendix 3
OR
 - b. A WOCBP who agrees to follow the contraceptive guidance in Appendix 3 during the treatment period and for at least 120 days after the last dose of study treatment.
4. Participant must have recurrent cervical cancer and have a low potential for cure with radiation therapy or surgery alone and:
 - a. May have received up to 2 prior chemotherapy regimens. Platinum sensitizing agents for radiation therapy are considered a chemotherapy regimen.
5. The participant (or legally acceptable representative if applicable) provides written informed consent for the trial, which includes compliance with the requirements and restrictions listed in the informed consent form (ICF) and this protocol.
6. Have measurable disease based on RECIST 1.1. Lesions situated in a previously irradiated area are considered measurable if progression has been demonstrated in such lesions.
7. Have provided archival tumor tissue sample or newly obtained core or excisional biopsy of a tumor lesion not previously irradiated. Formalin-fixed, paraffin embedded (FFPE) tissue blocks are preferred to slides. Newly obtained biopsies are preferred to archived tissue.

8. Have an Eastern Cooperative Oncology Group (ECOG) performance status of 0 to 1. Evaluation of ECOG is to be performed prior to the first dose of treatment.
9. Patient's life expectancy ≥ 16 weeks.
10. Have adequate organ function as defined in the following table (Table 1). Specimens must be collected within 10 days prior to the start of study treatment. Before patients can be enrolled, they must have normal laboratory values as outlined in Table 1. Labs must also fall within normal limits prior to infusion.

Table 1 Adequate Organ Function Laboratory Values

System	Laboratory Value
Hematological	
Absolute neutrophil count (ANC)	$\geq 1500/\mu\text{L}$

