7.0 STATISTICAL ANALYSIS PLAN

7.1 Statistical Analysis Plan Summary

7.2 Statistical Analysis Plan

Sample size calculation: Single-Stage design will be used for this study [A'Hern, 2001; Fleming, 1982]. The study will require 48 subjects to decide whether the proportion responding (P), is less than or equal to 0.130 or greater than or equal to 0.280. If the number of responses is 10 or more, the hypothesis that $P \leq 0.130$ is rejected with a target error rate of 0.100 and an actual error rate of 0.087. If the number of responses is nine or less, the hypothesis that $P \geq 0.280$ is rejected with a target error rate of 0.100 and an actual error rate of 0.099.

Efficacy analyses: The iORR will be defined as the proportion of patients with an “immune” complete response (iCR) or “immune” partial response (iPR). For the primary iORR analysis in all the treated population, patients with an iCR or iPR will be counted as successes and all other patients (including those with missing response information) will be counted as failures. The percentage of iORR with its 95% confidence interval (CI) will be presented.

Progression free survival (PFS) will be defined among all treated patients as the time from first dose of study drug until the first date of either disease progression or death due to any cause. The date of disease progression will be defined as the earliest date of disease progression based on central review. For patients whose disease has not progressed at the time of the analysis, censoring will be performed using the date of the last valid disease assessment. The data will be analyzed by the Kaplan-Meier method. The median PFS time and 95% CI will be recorded.

Overall survival (OS): Median OS will be defined as the time from the beginning of study drug treatment until death due to any cause. For patients who have not died at the time of the analysis, censoring will be performed using the date the patient was last known to be alive. The data will be analyzed by the Kaplan-Meier method. The median OS and 95% CI will be recorded.

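### Radiotherapy to a target lesion is possible on study, and no stated rule stops the resulting shrinkage from counting as a response in the primary iORR

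*Combined protocol and SAP*

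**What the plan says.** **Radiotherapy.** Section 5.5.2 lists radiation among the therapies barred in the Screening and Treatment Phase, followed by the Note: "Radiation therapy to a symptomatic solitary lesion or to the brain may be allowed at the investigator's discretion". Two tables in the same section also address it. Table 6 bars anticancer therapy while on study drug, with the entry "Radiotherapy (except palliative" and a closing bracket. Table 7 has a row on palliative use: "Palliative radiotherapy may be used for the treatment of pain at the site of bony metastases that were present at baseline". That row adds the condition that the pain must not, in the investigator's view, signal progression. Table 7 has study treatment restart within 4 weeks once marrow toxicity has recovered. Section 6.2.1.2 repeats that restart provision for radiation treatment without limiting it to bone.

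**Primary endpoint.** Under SAP 7.2, "patients with an iCR or iPR will be counted as successes" and everyone else is a failure. The decision is by count: 10 or more responses reject a true rate of 0.130 or below, at a target error of 0.100. The actual error rate is given as 0.087, with 48 subjects.

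**Irradiated lesions.** The one rule on measurability is inclusion criterion 6: "Lesions situated in a previously irradiated area are considered measurable if progression has been demonstrated in such lesions". It concerns entry. Appendix 4 mentions radiation only in defining clinical stability, which guides decisions at progression. Section 6.1.2.6 with its subsections, Appendix 4 and SAP 7.2 are silent on a lesion irradiated after baseline.

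**The concern.** A symptomatic solitary lesion can be a measurable target lesion, and 6.1.2.6 looks for only one lesion suitable as a target. In such a patient the irradiated lesion can make up the whole target sum. If it shrinks after radiation, the plan as written records an iPR or iCR. The confirmatory scan at least 4 weeks later (6.1.2.6.2) shows that the shrinkage lasted, not what caused it.

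The error runs in one direction, towards the regimen. There is no control arm in which the same thing would happen, and 6.1.2.6.6 has the investigator assess response. Because the verdict turns on a count with a sharp cut-off, one patient can decide it: 9 of 48 (18.8%) does not reject the null and 10 of 48 (20.8%) does.

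**Working it through.** **Inputs.** From SAP 7.2: n = 48, null rate 0.13, alternative 0.28, success declared at 10 or more responses, target error 0.100 on each side, actual errors 0.087 and 0.099. The number of patients who become responders through radiation is not in the documents, so it is an assumption below.

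**1. The plan's own figures.** With X binomial(48, p):
- P(X ≥ 10 | p = 0.13) = 0.0865, which agrees with the stated 0.087.
- P(X ≥ 10 | p = 0.28) = 0.9005, so the other error is 1 − 0.9005 = 0.0995, against a stated 0.099.

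The design is reproduced. It is also the smallest exact single-stage design that meets both 0.100 targets.

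**2. If k radiation-produced responders are certain.** The other 48 − k patients then need only 10 − k responses. At a true rate of 0.13:
- k = 0: P(X ≥ 10 | 48) = 0.087
- k = 1: P(X ≥ 9 | 47) = 0.150
- k = 2: P(X ≥ 8 | 46) = 0.243

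**3. If at most one such patient occurs, with probability π.** The error is a mixture:

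error = 0.0865 + π × (0.1498 − 0.0865) = 0.0865 + 0.0633π

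- π = 10%: 0.093
- π = 20%: 0.099
- error = 0.100 when π = (0.1000 − 0.0865) / 0.0633, about 21%

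**4. If every true non-responder carries the same small chance q of being miscounted.** The counted response rate is 0.13 + 0.87q.
- q = 1%: rate 0.1387, expected extra responders 48 × 0.87 × 0.01 = 0.42, error 0.120
- q = 2%: rate 0.1474, expected extra responders 0.84, error 0.161

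Steps 3 and 4 differ because q = 1% already implies 0.42 expected cases, twice the 0.21 at the threshold in step 3, and also allows more than one case. Both rest on an assumed frequency.

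**5. After the fix.** If a response obtained through an irradiated target lesion cannot count, n = 48, the cut-off of 10 and the stated error rates stand. The remedy is an endpoint rule and needs no new sample size.

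**The case against.** **Removal from study.** Section 5.5.2 says that participants needing a listed prohibited therapy should come off study, and that continuing needs agreement of investigator, sponsor and participant. These limits are real. But the Note reads as an exception to the prohibition, and the restart provisions in Table 7 and 6.2.1.2 show that irradiated patients can continue. Removal would not cancel an iPR under 7.2 either.

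**Clinical deterioration.** Section 5.8 makes a patient who deteriorates after two doses a treatment failure counted as progression. Some patients needing radiation may fall under this, but deterioration is not defined there and need not accompany one painful lesion.

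**Scope.** A reader might infer three conflicting permissions. That goes too far: Table 7's palliative row can be read as spelling out Table 6's exemption, so the two may form one rule. The clear discrepancy is between that rule and the Note, and only the Note plainly reaches a soft-tissue target lesion.

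**Screening.** A reader might see screening as an equally open route, because the baseline scan may precede allocation by up to 21 days (6.1.2.6.1) and exclusion 5 permits a 1-week washout after palliative radiation. The route exists but is narrow. Radiation in screening is barred apart from the Note, the usual washout is 2 weeks, and criterion 6 arguably disqualifies a lesion irradiated after the scan without later progression.

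**External criteria.** Section 6.1.2.6.6 and Appendix 4 refer to the iRECIST publication for further detail. It was not available here, so it cannot be checked for a rule on irradiated lesions. What can be said is that the plan states none.

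**Rarity.** A case needs discretionary irradiation of a target lesion that dominates the target sum, no progression elsewhere and a confirming scan. This objection stands, and it limits the size of the claim.

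**Conclusion.** The gap is real. Followed as written, the plan can score radiation shrinkage of a target lesion as a primary-endpoint success. The main route is radiotherapy during treatment under the 5.5.2 Note.

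It would be tempting to conclude that the stated error of 0.087 is wrong, or that the 0.100 limit is broken. The documents do not support that. The 0.087 is correct for the design, and the figures of 0.150 and 0.243 hold only if one or two such patients are certain to occur. No radiotherapy frequency is given and zero cases is plausible. If at most one can occur, the limit is passed only when its probability exceeds about 21%. All these figures also assume a true iORR of exactly 13% and that each affected patient would otherwise have been a non-responder.

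The point should be fixed, ideally before any response data are analysed, because it settles what counts as a success. It does not invalidate the sample size or the decision rule.

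**What to change.** Add to 6.1.2.6 and SAP 7.2:
- A target lesion given local radiotherapy after the baseline scan is not evaluable for response from the date of radiotherapy.
- An iCR or iPR first documented after that date is not a success in the primary iORR.
- A response first documented before radiotherapy counts only if the confirming scan also precedes it.
- Progression elsewhere still counts.
- A sensitivity analysis counts responses seen after radiotherapy.

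Record the site and date of any on-study radiotherapy on the CRF. Section 5.5.1 covers concomitant medication and 6.1.1.6.2 covers prior radiation, but no section expressly requires these on-study details.

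If a lesion is irradiated between the baseline scan and Day 1, re-check measurable disease under criterion 6 without that lesion. This also deals with the patient whose only target lesion was irradiated.

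Reconcile the 5.5.2 Note with Tables 6 and 7. Which clinical scope applies is for the sponsor to decide.

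**Cost.** A few sentences and one small CRF item. A few true drug responses may be counted as failures, which could lower the iORR slightly; the sensitivity analysis shows by how much.
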